8.2 Definition of Study Populations for Analysis

The following analysis populations are defined:

^{*} given that mean values were very similar, data from the class with the larger SD of weights was used

ADE = age-dependent exponent; BWp= body weight of children; CL/F= systemic clearance; F= Female; M = Male; ND= Not Done; SD = Standard Deviation

The **Full Analysis Set** (FAS) includes all patients randomized or to whom a study drug was assigned and who received a HEC or MEC regimen and the entire planned volume of netupitant and palonosetron. Following the intent-to-treat principle, patients will be assigned to the treatment group according to the treatment assigned/randomized. FAS will be used for demography, other baseline characteristics and efficacy analyses.

The **PK population** includes all patients who received the entire planned volume of netupitant and/or the entire planned volume of palonosetron and who have at least one measurable concentration of netupitant and/or palonosetron. PK population will be used for all PK analyses.

The **Safety** population includes all patients who received at least part of the planned volume of netupitant or at least part of the planned volume of palonosetron. Patients will be assigned to treatment groups according to the actual treatment received. Safety population will be used for demography, other baseline characteristics and for all safety analyses.

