5.2.2 Visit 2 (Day 1)

The following procedures will be performed/data collected:

- The patient will undergo pre-dose assessments, including confirmation of inclusion and exclusion criteria (local laboratory results from an appropriately certified local laboratory could be used at the discretion of Investigator to evaluate patients' eligibility; in case of ERT central ECG report pending, the assessment of compliance with exclusion criterion #21 could be made based on automatic interpretation of QTcB and QTcF results by ECG machine at the discretion of Investigator).
- Urine pregnancy test (for female patients having reached menarche only; if screening visit is performed on Day -1, it is not necessary to repeat the test on Day 1.).
- Concomitant medications and AEs recording
- Weight
- Treatment assignment / Randomization through IWRS.

After randomization/treatment assignment, the study drug administration schedule is the following:

- Netupitant will be administered based on the body weight as a single oral dose 1 h
 (± 10 minutes) prior to start of emetogenic (HEC or MEC) chemotherapy on Day
 1.
- Palonosetron will be administered orally immediately (within 5 minutes) after netupitant, i.e., 1 h (± 10 minutes) prior to start of emetogenic (HEC or MEC) chemotherapy on Day 1.
- Any LEC or minimally emetogenic agent given, as part of the aforementioned chemotherapy regimens using HEC or MEC, is allowed at any time during the study and does not have any impact on the time of study drugs administration.

The date and the precise time (hh:mm) of the study drug administration must be recorded in the source records as well as on the relevant eCRF page for each medication given. Information on completeness of study drug administration must be recorded as well. The relevant tear-off labels from the study drugs kit will be attached to the drug administration form.

- PK sampling: a single blood sample will be collected from each patient within the time window from 2 to 8 h after netupitant administration. Sampling will take into account the time of the 12-lead ECG and vital signs (see below).
- Vital signs (pulse rate, systolic and diastolic blood pressure) will be obtained 4-6 h after study drugs administration, before PK sampling or at least 30 minutes after PK sampling.
- A 12-lead ECG (single recording) will be obtained 4-6 h after study drugs administration, before PK sampling or at least 30 minutes after PK sampling.

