8.3.1 Missing Data

Due to the descriptive nature of the analysis, no procedure for handling missing data will be applied to pharmacokinetic or safety data.

For the efficacy analysis, any patients who do not provide data about occurrence of emetic episode and rescue medication intake after chemotherapy administration (which are needed to assess CR) will be considered as treatment failures in the relevant phase with missing information.

The same approach will be also applied to each component of CR, i.e. emetic episodes and rescue medication intake.

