8.3.5 Efficacy Analyses

All results will be interpreted in a descriptive manner, since the study is not powered to compare the treatment groups for the efficacy assessments.

For each phase (delayed, acute, and overall), numbers and percentages (including 95% CI) of patients with CR, with no emetic episodes and no rescue medication will be summarized by treatment. The difference in response rate between the groups and relevant 95% CI will be provided as well.

Efficacy analysis will be presented for the overall population and by strata.

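### The Full Analysis Set, the only set named for efficacy, admits only patients who took the whole volume of both study drugs

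*Protocol*

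**What the plan says.** Protocol Section 8.2 defines three analysis sets.

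- **FAS.** Patients who were randomized or had a study drug assigned, and "who received a HEC or MEC regimen and the entire planned volume of netupitant and palonosetron". On arm labels the paragraph adds: "Following the intent-to-treat principle, patients will be assigned to the treatment group according to the treatment assigned/randomized". On use: "FAS will be used for demography, other baseline characteristics and efficacy analyses".
- **PK population.** It "includes all patients who received the entire planned volume of netupitant and/or the entire planned volume of palonosetron" and who also have a measurable concentration. On use: "PK population will be used for all PK analyses".
- **Safety population.** Any part of either drug is enough. It serves demography, baseline and safety.

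No set other than the FAS is named for efficacy. Under Section 8.3.1, patients without the diary data needed for CR "will be considered as treatment failures in the relevant phase with missing information". Section 5.2.2 places dosing after randomization or treatment assignment and foresees incomplete intake: "Information on completeness of study drug administration must be recorded as well".

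**The concern.** A Full Analysis Set should stay as close as practicable to everyone assigned. Requiring the full volume of two oral liquids selects on something that happens after assignment and that may be related to outcome. That is how a per-protocol set is built.

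The intent-to-treat sentence does not repair this. Read strictly, it fixes the arm in which a patient is counted and says nothing about who is in the set. With that sentence beside the FAS name, a reader of the report could still take a rate in fully dosed patients for a rate in all treated patients.

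The efficacy tables are at stake: CR, no emetic episodes and no rescue medication, each for three phases, by dose and by stratum. Delayed-phase CR is also the efficacy parameter of the primary objective in a dose-finding trial, so a misdescribed denominator would be carried into later reading of the two doses.

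**Working it through.** **1. Who is in which set.** The Section 8.2 definitions, applied to patients who all received HEC or MEC:

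| Volume taken | FAS | PK population | Safety |
|---|---|---|---|
| All of both drugs | in | in, if a concentration is measurable | in |
| All netupitant, part of palonosetron | out | in, if measurable | in |
| Part of netupitant, all palonosetron | out | in, if measurable | in |
| Part of each | out | out | in |

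On dosing, the FAS is the strictest of the three. Patients in the last three rows appear in no efficacy table. Because they are outside the set, the failure rule of Section 8.3.1 cannot apply to them.

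**2. The plan's own figures.** The per-dose sample sizes in Section 8.1, with the 2 to <5 years class rounded up from 5 to 6, give 6 + 6 + 4 + 4 + 4 + 6 + 8 + 8 = 46 per arm. All eight stated powers (0.830 to 0.913) reproduce to three decimals. They concern the precision of clearance and do not depend on the FAS, so no sample size or power changes here.

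**3. Shift in a reported rate.** Let *k* of 46 patients in an arm be excluded for incomplete volume, *p* be the CR rate in fully dosed patients and *q* the CR rate in those excluded. The FAS reports *p*. The rate in all treated patients is [(46 − k)p + kq]/46. The difference is

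shift = (k/46)(p − q).

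The protocol gives no value for *k*, *p* or *q*. With assumed *p* = 0.55 and *k* from 2 to 9:

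| CR in excluded patients (q) | k = 2 | k = 9 |
|---|---|---|
| 0% | (2/46)(0.55) = +2.39 points | (9/46)(0.55) = +10.76 points |
| 55% | 0 | 0 |
| 70% | (2/46)(−0.15) = −0.65 points | (9/46)(−0.15) = −2.93 points |

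A positive value means the FAS rate is too high.

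**4. Bounds in whole patients.** Suppose 5 of 46 are incompletely dosed and 20 of the other 41 have CR (both assumed). The FAS rate is 20/41 = 48.8%. With all 46 kept, it is 20/46 = 43.5% if the five all fail and 25/46 = 54.3% if they all respond. With 2 of 46 excluded and 22 responders among 44, the FAS gives 50.0%, against 22/46 = 47.8% to 24/46 = 52.2%.

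**5. Dose difference.** If *p* and *q* are the same in both arms, the shift in the difference is ((k₂ − k₁)/46)(p − q). It is zero when the arms lose equal numbers. It is also zero when excluded patients respond like the rest.

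**6. Stratum tables.** Section 8.3.5 also presents efficacy by strata. One exclusion removes 1/4 = 25% of a dose-by-age cell in the three classes from 3 months to <2 years. It removes 1/6 = 16.7% in the two classes under 3 months and in 2 to <5 years, and 1/8 = 12.5% in the two oldest classes.

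**The case against.** The opposing case has several sound parts.

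- **Efficacy is descriptive.** Section 8.3.5 says so, "since the study is not powered to compare the treatment groups for the efficacy assessments", and the sample size rests on clearance. This stands and limits the weight of the point.
- **Bias between arms is unlikely to be large.** Treatment is a single dose given before chemotherapy, so intake is normally settled before the outcome window opens. In the randomized part, dosing is blinded and both strengths use the same weight-based volume (Section 4.8). In the youngest classes the first patients are assigned by escalation, so no randomized comparison exists among them. This stands for the dose difference. It does not help the rate within each arm, where a child who does not finish the dose may differ from one who does.
- **A full-dose condition suits an exposure-response study.** It can be reasonable for the PK/PD model, for which Section 8.3.6 names no set. That does not make the set a Full Analysis Set, nor does it justify it as the only set for the CR, no-emesis and no-rescue tables.
- **The magnitudes are assumed.** They are. The 10.8-point case combines 9 of 46 (19.6%) not completing a single dose with no response in any of them, and should be read as an outer limit.
- **The proposed set is not strict intent-to-treat either.** Receipt of HEC or MEC and of some drug also follows assignment. This is true, but it excludes far less on compliance than a requirement for two complete volumes.
- **Detail can be left to the SAP.** Section 8 leaves further detail there, but the FAS definition is fixed in the protocol itself.

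**Conclusion.** The point holds. The protocol states a rule that makes its only efficacy set a fully dosed set under a Full Analysis Set name. The efficacy rates therefore describe patients who completed both doses, not all who were assigned and treated.

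The direction of any error is unknown: rates are overstated if incompletely dosed patients respond less often, unchanged if they respond equally and understated if they respond better. Under the assumptions above, 2 exclusions per arm move a rate by −0.7 to +2.4 points, and 9 move it by −2.9 to +10.8 points. These figures rest on an assumed 55% CR and assumed exclusion counts, none of which the protocol supplies. The clearance-based sample size is untouched. This should be corrected, but it does not threaten the primary design.

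**What to change.** In Section 8.2, define the FAS as all patients randomized or assigned a study drug who received HEC or MEC and any amount of netupitant or palonosetron, analysed in the assigned group. Use that set for the efficacy tables in Section 8.3.5, so that the missing-data rule in Section 8.3.1 also reaches partly dosed patients.

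Keep the complete-volume set under a separate per-protocol name and repeat the efficacy tables in it as a sensitivity analysis. Report the number excluded for incomplete volume by arm and age class.

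The cost is a change of wording and one further set of efficacy tables. Completeness of administration is already recorded at Visit 2, so no new data are needed. Response rates may come out slightly lower if partly dosed patients do worse.

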8.3 Statistical Analysis

General Considerations

General descriptive statistics for numeric variables will include n (number of observed values), mean, standard deviation (SD), median, minimum and maximum values. For categorical variables, the number and percentage of patients will be presented.

8.3.1 Missing Data

Due to the descriptive nature of the analysis, no procedure for handling missing data will be applied to pharmacokinetic or safety data.

For the efficacy analysis, any patients who do not provide data about occurrence of emetic episode and rescue medication intake after chemotherapy administration (which are needed to assess CR) will be considered as treatment failures in the relevant phase with missing information.

The same approach will be also applied to each component of CR, i.e. emetic episodes and rescue medication intake.

8.3.2 Covariates, Interactions and Subgroups

There are some factors expected to influence the efficacy endpoints, i.e., age class, emetogenicity of chemotherapy and schedule of chemotherapy. These factors will be taken into consideration for randomization. Efficacy endpoints will be presented by strata.

8.3.3 Analysis of Demographics and Baseline Variables

Demographics and baseline characteristic will be summarized by treatment group by means of descriptive statistics, in addition to be listed. Descriptive statistics will be presented overall and by strata.

8.3.4 Pharmacokinetic Analysis

Exploratory PK analyses will be applied to evaluate in the pediatric population the disposition characteristics of netupitant, its metabolites and palonosetron observed in adult patients. The initial population PK model (base model) will be developed by comparing structural models and random error models based on parameters such as the objective function values, the log-likelihood values, the Akaike's and the Bayesian's Information Criteria (AIC and BIC), the residual errors, the random distribution in conditional weighted residual plots, the graphical correlation between the observed versus predicted concentration values.

The final population PK model will include possible additional fixed effects represented by relevant covariates that will prove to correlate with one or more population PK parameters and contribute to significantly explain and minimize the inter-subject variability.

The final model will be qualified via a visual predictive check.

Inter-subject / inter-occasion variability (level 1 random-effect) and observation-level random error (level 2 random effect) will also be modeled.

Individual model-predicted PK parameter values will be estimated from the final population pharmacokinetic models, based on mean population parameter values (TVs) and on the individual random effect (η i). Individual plasma-concentration-time curves will be simulated from final model parameters, and secondary parameters such as C_{max} , t_{max} , AUC and $t_{1/2}$ estimated by non-compartmental methods.

Mean and coefficient of variation (CV) of the pharmacokinetic parameters will be calculated from the individual predictions.

The effect of continuous and categorical covariates on the PK parameter variability will be evaluated by step-wise forward addition and backward elimination procedures. Continuous covariates will include at least age, BW, albumin, total bilirubin, creatinine, ALT, AST, ALP. Categorical covariates will include at least gender, chemotherapy schedule, HEC/MEC, rescue medication (yes/no), concomitant medications.

Adult data from previous population PK study NETU-10-02 [26] after oral administration of the netupitant-palonosetron fixed combination will be used as prior information and included in the analysis.

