Pharmacokinetic Analyses	Exploratory analyses will be applied to evaluate in the pediatric population the PK characteristics of netupitant (and its metabolites) and palonosetron after concomitant administration. The initial population PK models (base models) will be developed by comparing structural models and random error models based on

parameters such as the objective function values, the log-likelihood values, the Akaike's and the Bayesian's Information Criteria (AIC and BIC), the residual errors, the random distribution in conditional weighted residual plots, the graphical correlation between the observed versus predicted concentration values.

The final population PK models will include possible additional fixed effects represented by relevant covariates that will prove to correlate with one or more population PK parameters and contribute to significantly explain and minimize the inter-subject variability.

The final model will be qualified via a visual predictive check.

Inter-subject / inter-occasion variability (level 1 random-effect) and observation-level random error (level 2 random effect) will also be modeled.

Individual model-predicted PK parameter values will be estimated from the final population pharmacokinetic models, based on mean population parameter values (typical values, TVs) and on the individual random effect (η i). From final model parameters, individual plasma concentration-time profiles will be simulated and secondary PK parameters such as C_{max} , t_{max} , AUC and $t_{1/2}$ estimated by non-compartmental methods.

Mean and coefficient of variation (CV) of the pharmacokinetic parameters will be calculated from the individual predictions.

The effect of continuous and categorical covariates on the PK parameter variability will be evaluated by step-wise forward addition and backward elimination procedures. Continuous covariates will include at least age, BW, albumin, total bilirubin, creatinine, alanine aminotransferase (ALT), aspartate aminotransferase (AST), alkaline phosphatase (ALP). Categorical covariates will include at least gender, HEC/MEC, chemotherapy schedule, rescue medication (yes/no), concomitant medications.

Data from previous population PK study NETU-10-02 in adult cancer patients receiving oral NEPA FDC administration (300mg netupitant/0.5mg palonosetron) will be used as prior information and included in the analysis.

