4.10.3 Other Prior and Concomitant Medications

All medications used within 14 days prior to Day 1, or administered during the study as clinically indicated, are to be recorded on the appropriate electronic case report form (eCRF) pages. Prophylactic infusion of saline solution in order to prevent toxic reactions related to chemotherapy is to be recorded. Infusion of blood products has to be recorded. All medications administered in relation to diagnostic procedures (e.g., anesthetics, or antibiotics) are to be recorded.

According to protocol exclusion criterion #11, any investigational drug taken within 90 days prior to Day 1 for patients aged < 6 years, or any investigational drug within 30 days prior to Day 1 for patients aged ≥ 6 years, or through the entire study period are not allowed. For this purpose "Any investigational drug" has to be intended as a medication with no marketing authorization granted for any age class and any indication.

Based on exclusion criteria #13 and 14, the intake of any drugs or substances known to be strong or moderate inhibitors of CYP3A4 and CYP2D6 enzymes, including any of the narrow therapeutic range CYP3A4 substrates, within 1 week prior to Day 1 or use of such medications during the overall study period (until Visit 5 inclusive) is not permitted (Appendix 4).

Based on exclusion criterion #15, the intake of drugs or substances known to be inducers of CYP3A4 enzymes within 4 weeks prior to the dosing day or use of such medications during the overall study period (until Visit 5 inclusive) is not permitted (Appendix 4).

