4.11 Rescue Medication

Rescue medication should be administered to alleviate established, refractory or persistent nausea or vomiting and will be permitted on an as-needed basis.

Anti-emetic medications are not allowed as prevention of emesis, nor to increase the expected antiemetic effects of the study drugs, except for patients receiving HEC or MEC beyond Day 1.

Clinical Study Protocol

Rescue medication is defined as any medication taken to alleviate nausea or vomiting (i.e., with indication nausea or vomiting) during the period from start of emetogenic chemotherapy to 120 h later. The choice of rescue medication will be at the discretion of the Investigator. Investigator must ensure that rescue medication is made available to patients whenever needed.

Use of palonosetron or netupitant other than study drugs administration is not permitted.

Use of metoclopramide is not permitted as rescue medication.

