6.2.1 Primary Endpoint

PK/PD relationship between netupitant exposure (AUC, C_{max}) and antiemetic efficacy in the delayed phase after a single oral netupitant administration, concomitantly with oral palonosetron, in pediatric cancer patients receiving HEC or MEC treatments. Efficacy parameter to be used in the correlation is the proportion of patients with CR (i.e., no emetic episodes and no rescue medication) during the delayed phase (> 24-120 h after the start of chemotherapy on Day 1).

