8.3.6 Pharmacokinetic/Pharmacodynamic Analysis

PK/PD relationships between predicted individual exposure metrics (C_{max} and AUC) of netupitant versus efficacy (CR delayed phase) will be investigated via graphical exploratory analyses. In addition, a logistic regression analysis will be used to link the exposure metrics (C_{max} , AUC) to categorical response (CR delayed phase).

The dose-exposure relationship and the PK/PD correlation (exposure-response relationship) for netupitant in pediatric cancer patients will be compared to that observed in adult cancer patients in order to support the dose selection for netupitant in the pediatric population. Similar exposures in adult and pediatric patients are assumed to produce similar efficacy.

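### Rescue medication, a component of the delayed response, is a required candidate covariate in the netupitant PK model that supplies the exposures for the primary PK/PD regression

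*Protocol*

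**What the plan says.** Section 8.3.4 states: "Categorical covariates will include at least gender, chemotherapy schedule, HEC/MEC, rescue medication (yes/no), concomitant medications". The Pharmacokinetic Analyses row of the synopsis repeats the list in another order: "Categorical covariates will include at least gender, HEC/MEC, chemotherapy schedule, rescue medication (yes/no), concomitant medications". Both lists are minimum lists, so the SAP could not drop rescue without departing from the protocol. Covariate effects are to be "evaluated by step-wise forward addition and backward elimination procedures", with no entry or removal threshold given.

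The exposures come from the model that results. Section 8.3.4 says: "Individual model-predicted PK parameter values will be estimated from the final population pharmacokinetic models, based on mean population parameter values (TVs", and the sentence goes on to add the individual random effect. AUC and Cmax are then derived from the simulated individual profiles. In section 8.3.6, "a logistic regression analysis will be used to link the exposure metrics" (Cmax, AUC) to delayed CR.

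Section 6.2.1 makes this relation the primary endpoint: "Efficacy parameter to be used in the correlation is the proportion of patients with CR (i.e., no emetic episodes and no rescue medication", counted over the delayed phase (>24-120 h after chemotherapy starts on Day 1). Section 4.11 defines rescue as medication for nausea or vomiting taken "during the period from start of emetogenic chemotherapy to 120 h later", a window that contains the whole delayed phase.

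**The concern.** Any rescue in the delayed phase makes a child a non-responder. The yes/no flag has no stated phase, so apart from children rescued only in the first 24 h, rescue-yes implies delayed failure. The flag is thus largely a component of the response, and it is a mandatory candidate for building the predictor.

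Timing also argues against it as a determinant of exposure. Netupitant is given 1 h before chemotherapy (section 4.3), so delayed rescue falls more than 24 + 1 = 25 h after dosing. In healthy volunteers Cmax is reached at about 5 h (section 1.3.2.1). Delayed rescue cannot change a peak already past, yet a retained rescue effect, on clearance for example, could shift the predicted Cmax as well as the AUC.

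At stake is the exposure-response slope, which is the primary endpoint and one of the supports for dose selection. A final model containing rescue status also could not predict exposure for a new child without averaging over an event unknown at dosing.

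**Working it through.** **The protocol's own figures.** There are 60 planned children under 5 years with 3 samples each and 32 aged 5 or more with 4: 60×3 + 32×4 = 308, as section 6.1 states. That is 308/92 = 3.3 samples per child, so individual predictions will be shrunk. The eight powers in section 8.1 also reproduce to three decimals from P(t₀.₉₇₅,ₙ₋₁ · s/√n ≤ log 1.4), using the tabulated SDs of log CL/F. They do not depend on the covariate list.

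**Mechanism.** Let y be the log-exposure deviation that a child's samples show, and let r = 1 − shrinkage.

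- Without the rescue term, the prediction is ȳ + r(y − ȳ).
- With it, the prediction is ȳ_g + r(y − ȳ_g), where g is the child's own rescue group.

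If the observed group means differ by D, the predicted means differ by rD without the term and by D with it. The gap is multiplied by 1/0.8 = 1.25 at 20% shrinkage and by 1/0.5 = 2 at 50%. The groups being separated are largely the responders and non-responders of the next regression.

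**Simulation inputs.** From the protocol: n = 92 and a 3-fold dose ratio (4/1.33 and 2.4/0.8). Assumed, because the protocol gives no values: between-child SD of log exposure 0.4, shrinkage 20-50%, 50% delayed CR, 75% of delayed failures taking rescue. Rescue enters by a single likelihood-ratio test. CR is regressed on predicted log AUC (log dose plus predicted deviation), with and without the term on the same data, in 20,000 replicates per setting. The adult data that section 8.3.4 adds, and the competing covariates, are not modelled.

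| True slope per log AUC | Entry threshold | Rescue selected | Average rise in slope, all trials |
|---|---|---|---|
| 0.5 | p<0.05 | 8-10% | 1.5-3.6% |
| 0.5 | p<0.01 | 2-3% | 0.5-1.2% |
| 1.0 | p<0.05 | 17-23% | 1.9-4.5% |

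If 15% of delayed responders had acute-only rescue (slope 0.5, p<0.05), the average rise is 0.9-2.1%.

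**Trials that select rescue (slope 0.5, p<0.05).** The slope is 0.80 against 0.72 at 20% shrinkage (ratio 1.11) and 0.90 against 0.68 at 50% (ratio 1.32). The slopes without the term already exceed 0.5, so part of the excess over the truth reflects which trials are selected. The ratios isolate the effect of the term.

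**No true relation.** The rejection rate at a nominal 5% is 0.051-0.061, against 0.048 without the term. At p<0.01 entry it is 0.049-0.050. Simulation error is √(0.05×0.95/20,000) ≈ 0.0015.

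**Second null simulation, other assumptions** (40% any rescue, 80% of it delayed; 25% emesis; shrinkage 20-60%; 3,000 runs per setting). With both doses pooled, rejection is 0.050-0.060 when rescue is a candidate. Among runs where chance selected rescue it is 0.20-0.38, again partly because of which runs are selected. If rescue is always kept, it rises from 0.044 to 0.050, from 0.052 to 0.070 and from 0.054 to 0.092 at 20, 40 and 60% shrinkage.

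**The case against.** The strongest reply is that the effect is negligible in expectation. At a slope of 0.5 the average shift is about 0.004-0.018, against a sampling standard error of roughly 0.33 at n = 92; 0.018/0.33 is about 5% of one standard error. The written procedure also has backward elimination and admits only covariates that significantly explain variability. If the final threshold were p<0.001, the average rise would be 0.05-0.33% for slopes of 0.5-1.0. These points stand and limit the weight of the finding. They do not help the one trial that will be run if it retains the term.

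Second, with no true relation the distortion is symmetric: chance selection pushes the slope either way. That is right. Bias toward a stronger relation arises when a relation exists; otherwise the result is a slightly raised error rate.

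Third, section 8.3.6 attaches no alpha or decision rule to the regression, and dose support also rests on exposure matching with adults. True, but the relation is still the primary endpoint. The descriptive caveat in section 8.3.5 concerns comparison of treatment groups.

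Fourth, rescue might have a real PK role. For drug interaction, a yes/no flag names neither drug nor time, and section 4.10.3 already bars, through Visit 5, drugs "known to be strong or moderate inhibitors of CYP3A4 and CYP2D6 enzymes, including any of the narrow therapeutic range CYP3A4 substrates", as well as CYP3A4 inducers. Rescue might also mark early vomiting with lost absorption, which a covariate coded by interacting drug would miss. That is a fair reason to explore the flag, but only early rescue could play that role and the flag does not isolate it. It is no reason to let the flag feed the exposures.

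**Conclusion.** The concern holds. The protocol requires a post-dose component of the response to be tested for entry into the model that generates the predictor of the primary PK/PD regression, and no provision separates the two. The harm depends on selection and is incomplete because acute-only rescue is not a delayed failure. It is small on average but material in a trial that keeps the term. If exposure and response are truly related, the slope is exaggerated; if not, false positives rise slightly in both directions. All sizes rest on the assumed variability, shrinkage, response and rescue rates and entry thresholds, and on a two-stage approximation to the population model. The change is worth making because the problem is avoidable at no cost; it does not invalidate the design.

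**What to change.** In section 8.3.4 and the Pharmacokinetic Analyses row of the synopsis, remove rescue medication (yes/no) from the covariates of the netupitant model that supplies the exposures for section 8.3.6. Examine possible interactions through the concomitant-medications covariate already listed, coded by interacting drug and by start time relative to dosing and PK sampling, not by indication. An interacting drug that was given as rescue may still enter as that drug. If the flag itself is of interest, for instance as a marker of early vomiting, explore it in a separate sensitivity model whose predictions do not enter the PK/PD regression. The metabolite and palonosetron models need no change for this reason.

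The cost is wording in two places and one exploratory covariate fewer in the netupitant model. Sample size, sampling schedule and the stated powers are unchanged, and no clinical rule is affected.
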